6.3.5 Missed doses

A maximum of three doses may be given per week. If the dose was missed for more than 24 hours, the dose will be skipped and the next dose will be taken as per schedule. If the dose was missed within 24 hours, then it will be replaced. Doses should not be administered in less than 36 hours apart and all missed doses should be documented in the patient diary and the CRF.

6.3.6 Vomited doses

If a dose is vomited within one hour of ingestion, it will be replaced. If vomiting occurs more than 1 hour after dosing, it will still be considered a complete dose.

6.4 Concomitant Medication and Treatment

Concomitant medication is defined as any prescription or over-the-counter preparation, including vitamins and supplements. Patients may continue their baseline medication(s). All concomitant medication(s) must be reported in the case report form (CRF). Any diagnostic, therapeutic or surgical procedure performed during the study period should be recorded, including the dates, description of the procedure(s) and any clinical findings. Patients should minimize the use of products containing acetaminophen to less than 1000 mg acetaminophen on dosing days. Acetaminophen can interfere with the metabolism of Selinexor. For combination painkillers containing acetaminophen it is recommended that single agent opiates or aspirin combinations (when clinically acceptable) be substituted.

6.4.1 Permitted Concomitant Medication

Patients will receive concomitant medications to treat symptoms, adverse events and intercurrent illnesses that are medically necessary as standard care. Medications to treat concomitant diseases like diabetes, hypertension, etc. are allowed.

6.4.1.1 Prevention of Pregnancy

Female patients of child-bearing potential must agree to use dual methods of contraception and have a negative serum pregnancy test at screening, and male patients must use an effective barrier method of contraception if sexually active with a female of child-bearing potential. Acceptable methods of contraception are condoms with contraceptive foam, oral, implantable or injectable contraceptives, contraceptive patch, intrauterine device, diaphragm with spermicidal gel, or a sexual partner who is surgically sterilized or post-menopausal. For both male and female patients, effective methods of contraception must be used throughout the study and for three months following the last dose.

6.4.1.2 Use of Blood Products

During the administration of Selinexor, patients may receive red blood cell (RBC) or platelet transfusions, if clinically indicated, per institutional guidelines. Appropriate anti-coagulation is allowed during the study (eg: LMW heparin, direct factor Xa inhibitors, etc).

6.4.2 Prohibited Medications

Patients should minimize the use of products containing acetaminophen. For combination painkillers containing acetaminophen it is recommended that single agent opiates or metamizol combinations (when clinically acceptable) be substituted, particularly on the days of Selinexor dosing.

Concurrent therapy with an approved or investigational anticancer therapeutic, other than Ara-C, Idarubicin and glucocorticoids as specified herein, is not allowed.

Use of any immunosuppressive agents during the study must be confirmed by the Medical Monitor.

Other investigational agents should not be used during the study.

Inactivation of Selinexor by glutathione conjugation is a significant metabolic pathway *in vitro* and *in vivo*, including in humans. This process can be mediated in the absence of proteins, indicating that it is thermodynamically favorable. *In vitro* studies using human liver microsomes confirm *in vivo* findings that Selinexor undergoes minimal CYP450 metabolism. Therefore, administration of Selinexor with drugs which undergo substantial glutathione conjugation should be minimized or avoided. These drugs include acetaminophen (paracetamol) and ethyl alcohol. It should be noted that studies of Selinexor in combination with acetaminophen are to begin in late 2013 and therefore that these recommendations are empirical. It should also be noted that recreational ethanol ingestion is associated with glutathione depletion; therefore, the use of products containing ethanol should be minimized or avoided on Selinexor dosing days.

6.5 Supportive Care Guidelines

Supportive measures for optimal medical care shall be provided during participation in this clinical trial. Supportive care including anti-nausea / anti-emetic therapy, acid suppression (proton pump inhibitors and/or H2-blockers), glucocorticoids, and other standard treatments may be administered as per institutional guidelines for symptomatic patients. As needed and per individual study site institutional guidelines, prophylactic therapies, including antivirals, antifungals, and antibiotics, may be administered to ameliorate risks associated with non-malignant disorders or of immune system compromise.

All patients are required to receive prophylactic anti-emetics ondansetron 8 mg (or similar 5-HT3 antagonist) before their first dose of Selinexor and continued two or three times daily, as needed.

6.5.1 Anorexia

Based on clinical observations in over 1,175 adult patients treated with selinexor as of 31 May 2016, one of the most frequent treatment-emergent adverse event is anorexia (50%) with poor caloric and fluid intake leading to weight loss, fatigue and nausea. Therefore, it is strongly recommended that patients at risk for anorexia, weight loss, and/or fatigue receive strong nutritional counseling, high caloric beverages with adequate electrolyte levels (e.g., Ensure®), prophylaxis with appetite-stimulating agent(s), and anti-emetic agents. Patients with proper nutritional support and counseling have remained on Selinexor for >11 months. There is no correlation between initial BMI or weight and the development of anorexia.

In patients with problematic food/liquid/caloric intake, a patient log of food and drink should be considered and monitored by the treatment team.

Fresh juices, simple carbohydrates, as well as ginger can improve appetite before the meal; ginger may also improve dysgeusia.

Since the duration of treatment is short and most of the patients are hospitalized during induction treatment patients with anorexia nutrition is usually provided by infusion directly into the circulatory system

If constipation occurs, then laxatives should be given as constipation can contribute to anorexia and loss of appetite.

6.5.2 Fatigue

Fatigue may be related to underlying malignancy, Selinexor side effects, side effects of other agents or concurrent morbidities. Fatigue may also be related to anorexia and/or dehydration, so caloric and fluid intake should be optimized in all patients (please see above aggressive guidelines for maintenance of food and fluid intake). Acid suppression (proton pump inhibitors and/or H2-blockers) may be beneficial in some patients with fatigue.

6.5.3 Emesis

Supportive care for nausea and vomiting should be given promptly. The site can consider prophylactic treatment in case of previous side effect of nausea and vomiting with prior anti-cancer therapy. The treatment should start with the first sign of nausea. Standard anti-emetics are allowed and strongly recommended.

6.5.4 Acute Emesis

Acute emesis is not a major observation with Selinexor but has been reported. Selinexor associated nausea/emesis generally responds to D2-antagonists, 5-HT3 antagonists, or combinations of agents.

5-HT3 receptor antagonists (Zofran® 8 mg on days of dosing) — First-generation 5-HT3 receptor antagonists all appear equally effective at preventing nausea/emesis at the recommended doses. A single dose of a 5-HT3 receptor antagonist prior to therapy is equivalent to a multiple dose schedule. The efficacy of 5-HT3 receptor antagonists is significantly improved when they are combined with glucocorticoids. As QTc prolongation is the main side effect, magnesium and potassium should be corrected prior to use. If first-generation 5-HT3 receptor antagonists+dexamethasone do not adequately control emesis, second generation 5-HT3 receptor antagonists (e.g., palonosetron) should be considered. Second generation 5-HT3 receptor antagonists also improve delayed nausea/emeti response.

Neurokinin-1 receptor antagonists (e.g., aprepitant or fosaprepitant, Emend®) – should be considered in case of uncontrolled emesis with standard treatments as described above. Neurokinin-1 receptor antagonists should be given with combination of dexamethasone and first or second generation 5-HT3 receptor antagonists.

Additional treatment: Metoclopramide Hydrochloride 10mg, 30 min before meal (up to 4 time a day) or prochlorperazine (standard doses) have been effective in many patients. Dronabinol (Marinol) has shown some activity in both nausea/emesis and anorexia in patients treated with Selinexor. Lorazepam can be added to the combination treatment of 5-HT3 receptor antagonists +dexamethasone, e.g., at night, but has been less effective in Selinexor associated nausea/emesis.

6.5.5 Delayed Emesis - > 24h after treatment

Management — Selinexor is infrequently associated with delayed, resistant emesis. Many of the regimens associated with delayed emesis are classified as high-emeti risk, and professional guidelines recommend the use of an NK1 receptor antagonist (either NK-1 blockers e.g., aprepitant on days 1 to 3 or fosaprepitant on day 1 only), plus a glucocorticoids on days 1 to 4, along with a 5-HT3 receptor antagonist (particularly second generation agents) on day 1. This regimen is effective against both acute and delayed emesis. The data supporting the individual components of this regimen are reviewed below.

Olanzapine — Conventional antiemetics are more successful at preventing emesis than in preventing nausea, particularly delayed nausea. Olanzapine at the dose of 2.5 to 5 mg once daily (typically given at night to mitigate sedative effects) was proven effective in both anti emesis and nausea control. It may also be useful for management of breakthrough emesis, and to improve food intake in patients with anorexia.

Glucocorticoids are also consistently useful and should be administered as described above.

Granisetron transdermal patch — A transdermal preparation of granisetron should be consider in patients that have uncontrolled emesis/nausea >grade 2 under best supportive treatment

Ginger — Supplemental ginger added to foods or at doses of 0.5, 1.0gm powder daily total dose, usually in divided doses. Ginger may also improve dysgeusia.

Additional agents can be added, including lorazepam or alprazolam, a dopaminergic D2-antagonist (eg, prochlorperazine, thiethylperazine, haloperidol), or substituting high-dose intravenous metoclopramide for the 5-HT3 antagonist.

6.5.6 Diarrhea

Diarrhea is common at up to 27 % as of 31 May 2016 (mostly Grade 1), which responds to standard anti-diarrheal agents. Fluid replacement is important to prevent dehydration, fatigue and electrolyte abnormalities (e.g., hyponatremia).

6.5.7 Hyponatremia

Hyponatremia Grade 3 (plasma sodium < 130 nM) has been reported in 283 patients (24%) of patients treated with selinexor as of 31 May 2016: (please note that Grade 2 hyponatremia is not recognized in the CTCAE, v. 4.03; Grade 1 hyponatremia includes any plasma level between normal and 130 nM). None of the cases of Grade 3 hyponatremia was symptomatic and all were rapidly correctable with standard measures. No instances of Grade 4 hyponatremia have been seen. One case was pseudohyponatremia due to hyperglycemia (not associated with Selinexor). Most of the patients had anorexia, nausea, vomiting and/or diarrhea. Two of the patients with Grade 3 hyponatremia had third-space fluid accumulation or resolution (e.g., ascites, edema). Adequate fluid and caloric intake, including electrolyte rich beverages rather than free water, has led to reversal of the hyponatremia.

6.5.8 Liver enzyme increase

Liver toxicities in rodents and monkeys were not observed in the GLP toxicology studies. To date, significant liver toxicity has not been reported in patients treated with Selinexor. Patients should minimize their use of alcohol and acetaminophen as these drugs may deplete hepatic glutathione which could alter Selinexor metabolism. Studies of low dose acetaminophen administered just prior to Selinexor (in order to boost hepatic and gastrointestinal levels of Selinexor as demonstrated in rat nonclinical studies) are ongoing and will clarify any potential drug-drug interactions and/or liver toxicities of this combination. The secondary goal of these studies is to boost hepatic Selinexor levels in order to enhance hepatic anti-tumor activity. Glutathione (GSH) replacing agents such as N-acetylcysteine or S-adenosylmethionine may be considered if Selinexor induced liver dysfunction is suspected.

7 SAFETY REPORTING

The Investigator's Brochure will be used as reference document for KPT-330 (selinexor) and will be provided to the investigators in the investigator's file.

7.1 Adverse Events and Laboratory Abnormalities Reporting

7.1.1 Adverse Event

An adverse event is defined in the International Conference on Harmonization (ICH) Guideline for Good Clinical Practice as "any untoward medical occurrence in a patient or clinical investigation subject administered a pharmaceutical product and that does not necessarily have a causal relationship with this treatment" (ICH E6:1.2).

An adverse event can therefore be any unfavorable and unintended sign (including an abnormal laboratory finding, for example), symptom or disease temporally associated with the use of a medicinal product, whether or not it is considered related to the medicinal product.

7.1.2 Adverse Drug Reaction

All untoward and unintended responses to a medicinal product related to any dose administered.

The phrase "responses to a medicinal product" means that a causal relationship between the medicinal product and the adverse event is at least a reasonable possibility, i.e. the relationship cannot be ruled out.

A serious ADR (SADR) is an ADR that meets the definition of serious (provided below).

7.1.3 Serious Adverse Event

A serious adverse event (SAE) is defined as an adverse event that meets one or more of the following:

- is fatal
- is life threatening (places the subject at immediate risk of death)
- requires in-patient hospitalization or prolongation of existing hospitalization
- results in persistent or significant disability/incapacity
- is a congenital anomaly/birth defect
- other important medical events
- A hospitalization meeting the regulatory definition for "serious" is any inpatient hospital admission that includes a minimum of an overnight stay in a healthcare facility. Any adverse event that does not meet one of the definitions of serious (e.g. visit to A&E, outpatient surgery, or requires urgent investigation) may be considered by the investigator to meet the "other significant medical hazard" criterion for classification as a serious adverse event. Examples include allergic bronchospasm, convulsions, and blood dyscrasias.

Important medical events are defined as those occurrences that may not be immediately life threatening or result in death, hospitalization, or disability, but may jeopardize the subject or require medical or surgical intervention to prevent one of the other outcomes listed above. Medical judgment should be exercised in deciding whether such an AE should be considered serious.

7.1.4 NOT to be reported as SAEs

For this study, the following is **not** classified as serious adverse event:

- Progression or deterioration of the malignancy under study (including new metastatic lesions) or death due to progression.
- Hospitalization for the performance of protocol-required procedures or administration of study treatment. However, hospitalization or a prolonged hospitalization for a complication of therapy administration will be reported as an SAE.
- Hospitalization or procedures planned prior to study start. A pre-planned procedure must be documented in the source documents. However, hospitalization or prolonged hospitalization for a complication remains to be reported as an SAE.
- An elective hospitalization for a pre-existing condition unrelated to the studied indication.
- Hospital admission that is not associated with an adverse event (e.g. social hospitalization for purpose of respite care).
- Routine treatment or monitoring of the studied indication not associated with any deterioration in condition.
- The administration of blood or platelet transfusion as routine treatment of studied indication. However, hospitalization or prolonged hospitalization for a complication of such transfusions remains to be reported as an SAE.
- Emergency outpatient treatment or observation that does not result in admission, unless fulfilling other seriousness criteria above.

7.1.5 Adverse events of special interest (AESI)

The occurrence of acute cerebellar syndrome (ACS) and development of (or worsening of existing) cataracts during treatment with Selinexor are closely monitored as AESIs.

All cases of cerebellar toxicity \geq Grade 3 must be captured as an SAE and reported in an expedited Safety Report within 24 hours of awareness of the event.

7.1.6 SUSAR/ Unexpected Serious ADR

A SUSAR/ Unexpected Serious ADR is a suspected unexpected serious adverse reaction. A suspected adverse reaction is an adverse event for which there is a reasonable possibility that the drug caused the event. An unexpected adverse reaction is any adverse reaction with a reasonable possibility that the study drug caused the event and the specificity or severity is not consistent with the current investigator's brochure for Selinexor. Also, reports that provide significant information on the specificity or severity of a known, already documented adverse event constitute unexpected adverse events. An event more specific or more severe than described in the investigator's brochure would be considered "unexpected". All suspected adverse reactions related to Selinexor which occur in the trial and that are both unexpected and serious (SUSARs/ Unexpected Serious ADR) are subject to expedited reporting.

7.2 Reporting of SAEs

Any clinical adverse event or abnormal laboratory test value that is serious occurring during the course of the study from the date of signing the informed consent, irrespective of the treatment received by the patient, must be reported to the sponsor (via coordinating CRO) within 24 hours (expedited reporting). For each patient, all serious adverse events must be reported up to 30 days after the last dose of investigational product. Serious adverse events occurring more than 30 days after a patient is discontinued from the study treatment may be reported at the discretion of the investigator.

The completed SAE form must be faxed to:

GSO mbH

[contact]

The following detailed information must be recorded for each serious adverse event in the SAE report form:

- A description of the AE in medical terms according to NCI-CTC Version 4.03, not as reported by the subject
- The severity grade as assessed by the investigator according to the definitions in NCI-CTC Version 4.03
- The date of becoming serious and the date of becoming known (if different)
- The reason for seriousness
- The outcome of the SAE at the time of the report
- Information on administration of the study drug and chemotherapy and any action taken
- Information on any treatment procedures necessary for the SAE, concomitant medications, relevant lab tests and relevant medical history

If in any one subject the same SAE occurs on several occasions, then the SAE in question must be documented and assessed anew each time.

The investigator is required to submit SAE Follow-up reports until the SAE has resolved or stabilized and all queries have been answered.

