5.2.6 Follow-Up

Patients who discontinued for reasons other withdrawal of consent for participation in the trial will be followed every 3 months \pm 28 days event free and overall survival to assess the following:

- Relapse after CR or CRI
- Progression of disease in case of PR and non-responders
- Death
- Assessment of hematological recovery status until Platelet recovery $\geq 50 \times 10^9/L$ and $\geq 100 \times 10^9/L$, ANC recovery $\geq 0.5 \times 10^9/L$ and $\geq 1.0 \times 10^9/L$ is reached and date of recovery.

Follow-Up will be continued for maximum of 24 months per patient or end of study as defined below, whichever is first.

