7.3 Reporting of SUSARs/ Expedited Reporting of Unexpected Serious ADRs

The sponsor will via coordinating CRO ensure the notification of the appropriate ethics committees, competent authorities and participating investigators of all SUSARs events occurring at the sites in accordance with local legal requirements, statutes and the European Clinical Trial Directive as follows:

- Reporting of the SUSAR to the Competent Authorities and Ethics Committees within 15 days (or within 7 days for fatal and life-threatening events)
- Sending the event to all participating Investigators for information (with confirmation of receipt).
- In addition, all events that require a new assessment of the risk-benefit ratio will be reported to the Ethics Committee and the Competent Authority of each concerned Member State within 15 days. This includes:
 - Single reports of expected serious adverse reactions with unexpected outcome.
 - An increase in the rate of occurrence of expected serious adverse reactions which is judged to be clinically relevant
 - Post-study SUSARs that occur after the patient has completed a clinical trial
 - New events related to the conduct of the trial or the development of the investigational medicinal products and likely to affect the safety of the subjects

The sponsor is responsible to ensure that the latest investigator's brochure is used as the source document for determining the expectedness of an SAE.

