A serious adverse event occurring during the study or which comes to the attention of the investigator within three weeks of stopping the treatment or during the protocol-defined follow-up period, if this is longer, must be reported, whether considered treatment-related or not. In addition, serious adverse events occurring after this time should be reported if considered related to test "drug".

Such preliminary reports will be followed by detailed descriptions later that will include copies of hospital case reports, autopsy reports and other documents.

For serious adverse events, the following must be assessed and recorded on the adverse events page of the case report form: intensity, relationship to test substance, action taken, and outcome to date.

The obligation to document and report must be adhered to according to the national and international laws and regulations.

For contact details and fax no. for SAE and pregnancy reporting, please refer to Section [7.2](#).

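### Protocol 7.2 makes every SAE after 30 days optional, even if drug-related, while Appendix 3 asks for late SAEs; the two rules need reconciling

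*Protocol*

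**What the plan says.** Section 7.2 of the protocol gives three statements on timing. The first covers any serious event "occurring during the course of the study from the date of signing the informed consent". The second says that "all serious adverse events must be reported up to 30 days after the last dose of investigational product". The third says that SAEs "occurring more than 30 days after a patient is discontinued from the study treatment may be reported at the discretion of the investigator".

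Appendix 3 (section 17.3) sets a different rule. An SAE that occurs during the study, or that the investigator learns of "within three weeks of stopping the treatment or during the protocol-defined follow-up period, if this is longer, must be reported", and this applies whether or not it is judged related. It then adds that "serious adverse events occurring after this time should be reported if considered related to test" drug. Appendix 3 refers to section 7.2 only for contact details and states no order of precedence.

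Two other sections bear on this. Section 5.2.6 says "Follow-Up will be continued for maximum of 24 months per patient", or until end of study if that is earlier. Section 7.3 lists, among the events the sponsor will report to the ethics committee and the competent authority within 15 days, "Post-study SUSARs that occur after the patient has completed a clinical trial".

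**The concern.** A site that meets an SAE two months after a patient's last dose gets two answers. Section 7.2 lets the investigator decide, even if the investigator attributes the event to Selinexor. Appendix 3 tells the investigator to report it.

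What is at stake is the flow of late related events to the sponsor. A SUSAR is by definition a serious event suspected to be caused by the drug (section 7.1.6), so every post-study SUSAR starts as a late related SAE at a site. If sending that report is optional, the sponsor cannot be sure of meeting its commitment in section 7.3. Patients who go to transplant end study treatment before the transplant (sections 3.1.3 and 3.1.4), so much of their course may fall in the disputed period.

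**Working it through.** The plan gives no figure to reproduce. The check compares the texts and counts days.

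**Step 1: the two rules side by side.** Appendix 3 does not define its follow-up period. Reading A takes it as the follow-up phase of sections 3.1.5 and 5.2.6. Reading B takes it as the 30-day safety window of sections 5.1.3 and 7.2.

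| SAE | Section 7.2 | Appendix 3, reading A | Appendix 3, reading B |
|---|---|---|---|
| Any cause, to day 30 | required | required | required |
| Unrelated, day 31 to end of follow-up | discretionary | required | not requested |
| Related, day 31 to end of follow-up | discretionary | required | should be reported |
| Related, after follow-up | discretionary | should be reported | should be reported |

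The related rows disagree under both readings. The unrelated row disagrees only under A.

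**Step 2: size under reading A.** Follow-up of 24 months is 24 × 365/12 = 730 days. If it runs from end of treatment (the start is not stated), the period that is optional in one place and required in the other is at most 730 − 30 = 700 days per patient.

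End of study shortens this. Section 3.2 puts the end of enrolment in June 2016 and the end of study 2 years after the last registration, so about June 2018. For the last patient registered, follow-up after treatment is at most 730 days less the time on treatment (ignoring the up to two weeks between enrolment and first dose):
- one 28-day cycle: 730 − 28 − 30 = 672 days in dispute;
- the maximum 1 year of treatment: 730 − 365 − 30 = 335 days in dispute.

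Death or full withdrawal of consent shortens it further. Protocol version 3.1 is dated 13 January 2017, so about 17 months of the study remained when this text was issued.

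**Step 3: size under reading B.** Three weeks is 21 days and the safety window is 30, so the longer is 30 days. The all-cause windows then match apart from their start points. What remains is the related SAE after day 30.

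**Step 4: consistency within section 7.2.** The first sentence covers the course of the study, which under section 3.2 runs far beyond 30 days after treatment. The mandatory limit then counts from the last dose of investigational product, and the discretionary zone counts from discontinuation of study treatment. These dates can differ. In an induction cycle the last Selinexor dose is on day 18 of 28 (Synopsis, treatment scheme). If discontinuation is dated at the end of the cycle (an assumption), mandatory reporting stops on day 18 + 30 = 48 and the discretionary zone starts after day 28 + 30 = 58. Neither of those two sentences covers days 49 to 58.

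**Step 5: no other route for these events.** Table 2 in section 5.2 marks no adverse event or toxicity assessment in the follow-up column. Section 5.2.6 lists relapse, progression, death and blood count recovery. A non-fatal late SAE reaches the sponsor only if the site sends it.

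**Step 6: effect on the planned analysis.** The Synopsis, protocol section 5.1.3 and SAP section 13.1 all end adverse event capture 30 days after the last dose. A later SAE lies outside that window, so its absence leaves no gap in the planned summary. Deaths are a follow-up item, and the SAP states no 30-day limit for its summary of deaths by reason and relation to treatment.

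**The case against.** The strongest defence is that reading B is natural. Appendix 3 names the follow-up period next to a three-week limit after stopping treatment, which suggests a safety window. The 5.2.6 follow-up serves event-free and overall survival, and the schedule plans no adverse event assessment there. On that reading the all-cause rules nearly agree. This stands: the large gap is conditional. Against it, the only phase that the protocol itself calls follow-up is the one in sections 3.1.5 and 5.2.6.

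A second defence is that section 7.2 permits late reports, that its first sentence can be read as requiring them, and that Appendix 3 preserves duties under national and international law. This is fair as far as it goes. No document shows that a late related SAE was missed. But permission is not a duty, and the sentence on late events is the most specific one a site will find.

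A third is that Appendix 3 is headed as a set of ICH definitions and so is background. Its paragraph on timing, however, is an instruction to report, and it sends the reader to section 7.2 for where to send the report.

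A reader might also infer more than the documents support:
- **That 24 months of reporting is in dispute for all 40 patients.** That figure is a ceiling, it depends on reading A, and it is cut by end of study, death and withdrawal.
- **That Appendix 3 makes all late related SAEs mandatory.** It uses must for the follow-up period and only should afterwards.
- **That the safety summary will be incomplete.** The planned adverse event summary stops at 30 days by design.

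**Conclusion.** The conflict is real and does not depend on interpretation where it matters most: a related SAE after day 30 is optional under section 7.2 and requested under Appendix 3, with no rule on which prevails. For all-cause SAEs the disagreement ranges from almost nothing (reading B) to at most about 700 days per patient (reading A, with follow-up counted from end of treatment). Section 7.2 is also inconsistent in its scope and in its start point.

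The consequence is for SAE and SUSAR reporting. The primary endpoint and the planned 30-day adverse event tables are not affected. The point should be corrected, but it is a matter of protocol wording and does not threaten the trial's main conclusion.

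**What to change.** Reconcile section 7.2 with Appendix 3:

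1. State one window for all-cause SAEs, with one start point (last dose or discontinuation, not both), in the same words in both places. Align the first sentence of 7.2 with it.
2. If the Appendix 3 wording on follow-up is kept, say which period it means. If that is the 5.2.6 follow-up, add an SAE enquiry to the follow-up column of Table 2, so that the duty has a matching collection step.
3. In section 7.2, remove the investigator's discretion for SAEs considered related to Selinexor, in line with what Appendix 3 and section 7.3 already say.

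The length of the all-cause window is for the sponsor to decide; the documents do not settle it. The cost is protocol wording, a letter to the 6 to 8 sites and a few more SAE forms. Section 7.1.4 already excludes progression and death due to progression from SAE reporting, which keeps the number of extra forms down.
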